After being determined to fit into an available cell category, thus filling the target population of the U.S. workforce, the remaining screening components assess the subjects' abilities to wear a respirator and perform the required exercises safely. The medical screening components seek a subject population without chronic health problems that may increase the risk when exercising or wearing a respirator. These risk factors may be self-reported by the subjects or physiologically measured.

Subjects will complete the OSHA/NPPTL Medical Evaluation form (Appendix D), the NPPTL Screening Medical Evaluation (Appendix E), and the NPPTL Subject Data Form (Appendix F). Subjects that would like to participate in more than one Phase of this study, which may lead to > one year involvement, will be re consented and re-screened at minimum yearly, as is standard in human subject's research, for collection of potential baseline result changes, for example facial dimension, weight, and maximal heart rate. Because OSHA has determined that fit testing of respirators must be completed annually at minimum due to potential changes in baseline measurements and medical considerations, we will use their suggested length of time determined by OSHA research and expertise in this arena, to base our re-screening timeframe, in the event a subject participates for > one year. Additionally, a yearly medical evaluation has been established in the NPPTL Protocol for Human Subject Testing for Respirator Inward Leakage (IL) (HSRB 14-NPPTL-02).

However, we will additionally at every study visit during each calendar year review changes in health and wellbeing with subjects prior to testing, to also reduce risk in between re-screening each year. If during a routine visit within a calendar year from date of screening, a subject is found to have medical and/or physical changes from baseline that may increase their risk to participate (based on Pre Visit Medical Evaluation with the medical monitor CRNP), consideration for early re-screening or participant discontinuation will be reviewed by medical monitor CRNP and study team.

Figure 2. NIOSH panel based on face length and face width

Face Width (mm)

	138.5	120.5	134 132.5	4.5 144	146.5 4.5	158	3.5
	128.5	6 (2)		9 (2)		10 (2)	
th (mm	118.5	6 (2)	·	7 (4)		8 (2)	
Face Length (mm)	108.5	3 (2)		4 (5)		5 (2)	
Fac	98.5	1 (2)		2 (2)		U (2)	

Table 2. Percentage of Population and Number of Subjects by Cell for the Panel

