3.2 Phase I

Phase I is designed to test a novel healthcare practice-based exercise regimen for SWPF testing of PAPRs with 25 evaluable subjects that represent the US workforce facial measurements. In this phase, subjects will not wear PAPRs, however they will complete one 30-minute regimen that includes ten, 3-minute exercises to determine Work Rate category allocation per exercise. The simulated workplace exercises were created based on: a) exercises from ANSI (American National Standards Institute) and OSHA respirator test protocols (ANSI, 2010; CFR, 1998); and b) routine healthcare activities (Table 3.). This phase will be completed without PAPRs and subjects will have physiological measurements taken with a metabolic cart. During each exercise regimen replicate subjects will be equipped with a heart rate (HR) monitor and siliconerubber oronasal facemask from the metabolic cart. Expired air sample will be analyzed for oxygen uptake (VO₂), minute ventilation (V_e), and carbon dioxide (VCO₂).

25 subjects x 1 regimen x 3 replicates = 75 max oxygen uptake (VO₂) and 75 max heart rate (HR) values per exercise to determine work rate category allocation (Table 4.). In this study phase, the data will be analyzed after all 25 subjects complete the first of three attempts so that each exercise will have 25 values calculated. Subjects will complete all consent and screening items, along with the first replicate of Phase I during their first visit (~3 hours) and will complete the second and third replicates on a different visit (~3 hours). Phase I will be conducted in conjunction with screening and completed over 2 visits (~6 hours total). It is anticipated that all subjects will complete Phase I/screening in 3-6 months (July 2019-December 2019).

Mean Population Parameter with 95% (1.960) confidence interval will be used to analyze data. For each exercise, if the 95% confidence interval is within theoretical bounds for each work rate, then the second and third replicates will not need to be completed and Phase II of this study will begin. The theoretical bounds can be found under the relative intensity columns in Table 4.

Hypothesized Work Rates

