8	Bending and Picking up weight: bending to pick up two weighted bags equipped with a handle (5-lb bag/each hand) and carrying them from side-to-side of the testing chamber at a moderate walking pace, then bending to put down weights. Repeat for 3 minutes.	3	Hard
9	Perform CPR/AED: perform CPR on a training manikin by compressing chest cavity ~1.5 - 2 inches at a rate of 80-100 compressions/min. 2 min of CPR followed by 1 minute of AED use.	3	Hard

10	Stair climbing: stair climbing (using a 3-step ladder) climb rate ~ 10-12 cycles/min (one cycle = up 3 steps and back down 3 steps).	3	Hard	
----	---	---	------	--

362

363 364 365

366 367 368

369 370

371

372

382

387 388 389 Work Rates

Average work rates will be determined for each individual exercise for each subject, and the mean values will be then calculated for each exercise for all 25 test subjects. Work rate classifications are listed in Table 4 below (American College of Medicine, 2013).

Table 4. Work Rate Classifications for Physical Activities

	Relative Int	ensity	Absolute Intensity Ranges (METs) Across Fitness Levels			
Intensity	VO₂R (%) HRR (%)	Maximal HR (%)	12 MET VO _{2max}	10 MET VO _{2max}	8 MET VO _{2max}	6 MET VO _{2max}
Very light	<20	<50	<3.2	<2.8	<2.4	<2.0
Light -	20-39	50-63	3.2-5.3	2.8-4.5	2.4-3.7	2.0-3.0
Moderate	40-59	64-76	5.4-7.5	4.6-6.3	3.8-5.1	3.1-4.0
Hard (vigorous)	60-84	77-93	7.6-10.2	6.4-8.6	5.2-6.9	4.1-5.2
Very hard	≥85	≥94	≥10.3	≥8.7	≥7.0	≥5.3
Maximal	100	100	12	10	8	6

The information from the GXT (Appendix K) has a screening purpose and a research purpose. It will be used for 1) safety screening prior to participation and establishment of test termination criteria (Section 7.4) and 2) relative workload determination for the desired work-related activity in Table 3. Work rates in Table 4 will be determined for each exercise as a percentage of the subjects' maximum oxygen uptake and maximum heart rate, both of which are measured during

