Additionally, subjects will perform a maximal graded exercise test (Appendix K) with a treadmill using Bruce protocol (Wasserman, 2012). Testing will provide a baseline health review to promote reduced risk of clinically contraindicated signs or symptoms for exercise studies included in this protocol. Subjects must achieve a maximal oxygen consumption of "Fair" to "Excellent" score during this test based on recommendations for exercise testing safety from the American College of Sports Medicine Fitness Categories for Maximal Aerobic Power (treadmill test). During this test Maximal Heart Rate and Maximal Ventilated Oxygen will be obtained to provide individual subject safety parameters that will be used during study interventions. Additionally, a continuous electrocardiogram (EKG) will be completed and assessed by a U.S.

licensed health professional to determine if any unknown underlying arrhythmias or heart conditions that would exclude the subject from participation during the Bruce protocol.

Active Study Evaluations

Once a subject is eligible and registered for the study, daily pre and post visit medical evaluations, as well as monitoring by a U.S. licensed health professional intra testing, will be conducted on the NPPTL campus in a designated laboratory to aid continued safety and prevention of exercise induced adverse events. A NPPTL Pre Visit Medical Evaluation form (Appendix L) will be completed by a U.S. licensed health professional with each subject at the start of each study visit to promote safety. A NPPTL Post Visit Medical Evaluation form (Appendix O) will be completed by a U.S. licensed health professional with each subject at the conclusion of each visit, and subject will not be discharged until the U.S. licensed health professional subject safety. Supplemental nourishment in the form of milkshakes (i.e., Ensure®) or sports drinks (i.e., Gatorade®) will be available in the NPPTL Physiology Laboratory/Building 40 laboratory to assist in hydrating the subject if needed (e.g., cold Gatorade®, cold bottled water).

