$HR \geqslant 90\%$ of measured HR_{max} for a period of at least one minute	X	X	X	X	X	
At the discretion of the investigator/ U.S. licensed health professional	X	X	X	X	X	
[CO ₂] in the PAPR \geq 6% of atmospheric by volume for a period greater than one minute			X	X		

Maximal aerobic capacity (VO_{2max}) of subjects is monitored as part of the screening process and to provide safety during study interventions. The screening maximal graded exercise test includes the determination of underlying cardiopulmonary issues that may exclude the subject for safety purposes. Additionally the Maximal Graded Exercise test will allow the study team to determine the level of exercise at which the subject reaches their maximal oxygen uptake (VO_{2max}). If VO_{2max} has been reached, as determined during screening, the study team will terminate the exercise and remove subject from study to promote safety. The maximal heart rate achieved at VO_{2max} is also measured during the maximal graded exercise screening test. If the subject reaches $\geq 90\%$ of their maximal heart rate (HR_{max}) over the course of one minute, the study test will be terminated and the subject removed from study for safety. For example, if the subjects HR_{max} is $190 \text{ b} \cdot \text{min}^{-1}$, the test would be terminated when the subjects HR reaches $171 \text{ b} \cdot \text{min}^{-1}$ over the course of one minute during testing. The procedure for the Maximal Graded Exercise Test, as well as monitoring from the metabolic cart, is described in Appendix K.

During Phases II and III, subjects will be breathing in a confined space with an expected increase in atmospheric CO₂, leading to a potential for CO₂ rebreathing. For this reason, a test termination criterion has been established as a function of in-mask change in CO₂ concentration from atmospheric levels. If the in-mask CO₂ concentration is greater than 6% of the atmospheric levels, for a period greater than one minute, the test will be terminated.

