APPENDIX K. MAXIMAL GRADED EXERCISE TEST (GXT)

This screening test will be conducted according to the Bruce protocol (table below). Subjects will begin by walking on a treadmill at 1.7 mph at 0%, 5%, and 10% grade for 3 minutes at each grade. Then, the treadmill speed will be increased by 0.8 mph and the grade by 2% every 3 minutes until the speed reaches 5.0 mph and the grade reaches 18%. The speed will continue to increase by 0.5 mph every 3 minutes, but the grade will remain the same for the remainder of the test. Subjects will complete as many stages until volitional fatigue.

Bruce Protocol

Stage	Duration (min)	Treadmill Speed (mph)	Treadmill Grade (%) 933
1	3	1.7	0 1634
2	3	1.7	5 1635
3	3	1.7	10 1636
4	3	2.5	12 1637
5	3	3.4	14 1638
6	3	4.2	16 1639
7	3	5.0	18 1640
8	3	5.5	18 1641 18 1642
9	3	6.0	18 1643

Subjects will be equipped with a heart rate (HR) monitor and silicone-rubber oronasal facemask from the metabolic cart (K5 Wearable Metabolic Technology) (Cosmed, Rome, Italy) during the Maximal Graded Exercise Test. The metabolic cart, authorized for use by NPPTL physiology lab personnel, is device that measures expired air for oxygen uptake (VO₂), minute ventilation (V_e), and carbon dioxide (VCO₂).

Subjects will be placed into the one of the categories described in Table 4 following this test. Subjects who achieve a maximal oxygen consumption above "Poor" category (e.g. Fair to Excellent categories) based on American College of Sports Medicine Fitness Categories for Maximal Aerobic Power (treadmill test) maybe included in the study.

Subjects will be equipped with an EKG during this test to detect and potential abnormal responses to exercise (e.g., life-threatening dysrhythmias, ventricular tachycardia, ST-T waves changes, or any evidence of ischemia). The reason for the EKG being taken during the test is to identify potential abnormal cardiovascular conditions that otherwise may not be visible on an EKG taken at rest.

Subjects' blood pressure will be monitored once during each stage of this protocol. Any abnormal blood pressure response to exercise (e.g. hypotensive response) will result in test termination.

The termination of this test will be carried out with a gradual walking down of the treadmill grade and speed, as to avoid injuries to the subjects. Following GXT, subject will be given water as much they want.

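### Table 7 applies the 90%-of-HRmax stop to the maximal test that measures HRmax, and sections 7.3 and 7.4 disagree on what follows when the limit is reached

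*Protocol*

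**What the plan says.** Table 7 in section 7.4 lists a stop when heart rate is at or above 90% of measured HRmax "for a period of at least one minute". The row is marked in all five columns: Screening, Phases I, II and III, and the pre/post-test evaluation.

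The text below the table says that HRmax is measured in the screening GXT. On reaching 90% of it for a minute, "the study test will be terminated and the subject removed from study for safety". A parallel sentence covers VO2max: if it has been reached, "as determined during screening, the study team will terminate the exercise and remove subject from study to promote safety".

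On the GXT itself, Appendix K states: "Subjects will complete as many stages until volitional fatigue". Section 7.3 says that its maxima are obtained "to provide individual subject safety parameters that will be used during study interventions". Section 4.1 makes completing it an inclusion criterion. Section 3.1 requires re-screening at least yearly, "for collection of potential baseline result changes, for example facial dimension, weight, and maximal heart rate".

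In the caffeine rationale, section 7.3 says that exceeding the study's heart-rate limit ends the test and excludes the subject for that day.

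**The concern.** A limit defined as a fraction of a measured maximum should not also govern the test that measures the maximum. Where an earlier HRmax exists, the rule as marked ends the repeat test before a new maximum is reached, although section 3.1 gives re-measurement as a reason for re-screening. At stake are the updated stopping limits for later visits and the VO2max category that section 4.1 uses for eligibility.

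The second problem is disposition. A subject removed from the study cannot finish the phase; a subject excluded for the day can return and finish. The Protocol Summary counts a subject as evaluable only on completing all interventions of at least one phase, so the two wordings can produce different sets of evaluable subjects. Staff applying the rule cannot tell which one to follow.

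**Working it through.** **The Screening mark.** Table 7 does distinguish between phases. The EKG row is marked for Screening only, the VO2max row for Screening and Phase I, and the CO2 row for Phases II and III. The heart-rate row has five marks for five columns, so on its face the Screening mark is an instruction. The only exercise test at screening is the GXT.

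**The protocol's own figure.** With HRmax = 190 beats/min, 0.90 x 190 = 171 beats/min. This matches the worked example in section 7.4.

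**First GXT.** The rule needs a measured HRmax and none exists, so it cannot operate. The test runs to Appendix K's endpoint. HRmax, VO2max and the Phase I percentages built on them are unaffected.

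**Re-screen GXT.** Suppose the earlier HRmax is 190. The rule stops the test after one minute at or above 171. It has no effect only if the subject fatigues before completing that minute.

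Table 4 shows roughly how far short of maximum this is. In the Hard row, 77-93% of maximal heart rate corresponds to the listed MET ranges. Assuming linearity within the row, 90% lies (90 - 77)/(93 - 77) = 0.8125 of the way up:

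| VO2max (METs) | METs at 90% HRmax | Below maximum |
|---|---|---|
| 12 | 7.6 + 0.8125 x 2.6 = 9.71 | 19.1% |
| 10 | 6.4 + 0.8125 x 2.2 = 8.19 | 18.1% |
| 8 | 5.2 + 0.8125 x 1.7 = 6.58 | 17.7% |
| 6 | 4.1 + 0.8125 x 1.1 = 4.99 | 16.8% |

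If heart rate has climbed to 93% by the end of the minute, the top of the row gives 10.2, 8.6, 6.9 and 5.2 METs, which is 15.0%, 14.0%, 13.7% and 13.3% below maximum. On this interpolation the stopped test falls about 13-19% short of VO2max.

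**Who could be exposed.** Screening is planned for July-December 2019 (section 3.2) and Phase III for April-September 2020 (section 3.4). On those dates the yearly rule reaches subjects screened in July-September 2019 who are still active at their anniversary in July-September 2020. Section 3.1 also allows early re-screens after a health change. The protocol does not say how many subjects that is.

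**Disposition at the limit, side by side.**
- Section 7.4: test ended, subject removed from the study.
- Section 7.3: test ended, subject excluded for the day.
- Section 6.0: lists reasons for which subjects may be removed; the heart-rate limit is not named among them.

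**The case against.** The strongest reply is that the Screening mark is blanket marking that nobody would enforce. The same row is marked for the pre/post evaluation, where vital signs are taken at rest, and the VO2max row already gives the GXT a proper endpoint. Exposure is also small: the Appendix A footnotes tie re-screening to registering more than a year after Phase I registration, and Phase III starts less than a year after the first screenings. This lowers the severity, but the mark remains, and section 3.1's yearly minimum can still reach late subjects.

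On disposition, one can say that the section 7.3 phrase only explains the caffeine rule. Even so, it states a consequence for exceeding the limit, and it differs from the one in section 7.4.

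Three stronger readings are tempting and are not supported:

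- **That the VO2max sentence removes subjects for completing the GXT.** Section 7.3 says the maxima are for use in later interventions. Appendix L carries the screening values forward as each visit's safety parameters, and Appendix O asks whether they were reached in that day's tests. Together these largely settle that screening supplies the limit and later regimens apply it.
- **That later limits would ratchet down.** If a truncated peak of 171 were recorded as HRmax, the next limit would be 0.90 x 171 = 153.9 beats/min, or 81% of 190. No section directs that recording. Section 7.4 defines HRmax as the rate achieved at VO2max, which a truncated test does not reach.
- **That Phase I work rates are biased because the 90% limit lies inside Table 4's Hard band.** This needs permanent removal plus an assumed heart-rate distribution for the hard exercises. The protocol gives no means or SDs, so neither a bias nor its size can be established.

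**Conclusion.** Two statements are wrong as written: the Screening mark in the Table 7 heart-rate row, and the conflicting consequences in sections 7.3 and 7.4. Followed literally, the mark prevents a valid re-measurement of HRmax and VO2max at a re-screen GXT. The conflict leaves open which subjects can remain evaluable.

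Severity is minor. The effect of the mark assumes that staff enforce it and that the GXT is repeated at re-screening, as section 3.1 implies. The 13-19% shortfall rests on linear interpolation in Table 4 and on the earlier HRmax still being the true one. It shows how far below maximum the test would end and does not predict recorded values.

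**What to change.** - Delete the Screening mark in the heart-rate row of Table 7, with the medical team's agreement. Appendix K's endpoint and the symptom, EKG, blood pressure, oxygen saturation and investigator-discretion stops then govern the GXT. The Screening mark in the VO2max row can stay as the test's endpoint.
- Word the heart-rate and VO2max stop sentences in section 7.4 as applying to the study exercise regimens, with VO2max limited to Phase I as Table 7 has it. Appendices L and O already imply this.
- State one consequence of the heart-rate limit in both sections 7.3 and 7.4. One option is to stop the test, end the visit and require medical review before return. If permanent removal is intended, say so in both places.

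The cost is one table mark and a few sentences, with no added subjects, visits or procedures. The trade-off is that a re-screened subject again exercises to maximum without a heart-rate cap, as at the first GXT, which is why the medical team must agree.

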3.3 Phase II

the GXT.

Phase II is designed to test flow rate effects on individual exercises & regimen overall SWPF values. This phase will include the 25 evaluable subjects from Phase I if they are interested in continued participation. If subjects from Phase I decline or are no longer eligible, additional subjects may be consented and screened for recruitment utilizing the modified screening requirements from Phase I (Appendix A, Study Calendar 1). Phase II will use the exercise regimen (Table 3.) and work rates determined in Phase I, with eight different PAPR models and two flow rates for each PAPR. Subject's will complete one 30-minute regimen = ten, 3 minute exercises completed in sequential order from light to hard work rates with breaks following the hard exercises (see Section 3.2) for sequence. 25 subjects x 8 PAPR models x 2 flow rates x 2 regimen replicates = 800 overall SWPF values (based on 10 exercises). Three Way Repeated Measures ANOVA will be used to analyze the data.

Each subject will come in to test 2 PAPRs and 2 flow rates per visit for approximately 3 hours, 392 for a total of 4 visits (~12 total hours) to complete the first replicate of tests. The subjects will 393 repeat the same procedure for the second replicate, meaning each subject will complete Phase II 394 over the course of 8 visits of approximately 3 hours per visit (~24 total hours). It is estimated that this phase will take 6 to 9 months (November 2019-July 2020). 396

PAPR Models

391

395

397

398

399

400

401

402

403

404

405 406

407

408 409

410

Eight PAPR models (4 PAPRs with loose-fitting hoods, 2 loose-fitting facepiece PAPRs with helmets, and 2 tight-fitting PAPRs) were selected for this study (Table 5.). The models were selected based on: 1) prevalence of respirators in healthcare (Wizner, 2016) and 2) their commercial availability. The assigned protection factors for each PAPR is 25 or 1000. Tight fitting full facepieces (models 1-2) have a tight seal along the chin and sides of face. Loosefitting full hoods (models 3-6) have a shroud covering the shoulders down to the mid-torso. Loose-fitting facepieces (models 7-8) have a cuff that loosely contacts the chin and the sides of the face. Each PAPR device weight will be measured and recorded. All PAPR devices used in this study will be set at the same airflow rate. Each subject will be asked to complete the comfort survey after each PAPR tested with all three flow rates in Phase II (Appendix M).

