During testing subjects will be equipped with a fingertip-pulse oximeter (AG Industries, St. Louis, MO) to monitor oxygen saturation information during testing. If the subject's O₂ saturation level goes below 90%, the test will be terminated. Subjects will also be equipped with a differential pressure line and a CO₂ line for monitoring CO₂ accumulation in the RIC. A CO₂ gas analyzer (CD-3A carbon dioxide analyzer and S-3A/I oxygen analyzer, AEI Technologies, Chicago, IL (or equivalent) will be used to continuously monitor CO₂ gas (percentage by volume) inside the PAPR facepiece during SWPF testing. The PAPR facepiece will be fitted with a sampling probe; flexible tubing will transport the in-mask sample to the CO₂ analyzer which will be located outside of the corn oil chamber.

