- *CO*₂ *rebreathing:* If in the rare event the in-mask CO₂ concentration is greater than 6% of the atmospheric levels, for a period greater than one minute, the test will be stopped for safety. This could be caused by the confined spaces of the respirator and/or reduced airflow respirator modification.
- Contact Dermatitis: The respirator or monitoring equipment may cause a sensitivity reaction in a minority of participants. Participants will be instructed to inform study personnel if they develop or suspect redness or irritation on their body, face, scalp, and/or neck
- Claustrophobia: Attributed to equipment wear, is rare and may occur in a minority of
 participants. Participants will be instructed to remove their device inform study
 personnel if this occurs. This could be caused by the confined spaces of the respirator
 and/or reduced airflow respirator modification.

Risk of Breach of Confidentiality. In very rare cases, people not associated with this research study may inadvertently see subject's identifiable research results. This could result in

psychosocial discomforts or difficulties. The researchers will try to prevent this from happening by keeping all research records in locked buildings and within secured server software systems accessible only by Personal Identification Verification badges.

Economic Risk. It is possible that subjects may experience financial costs, in the form of treatment-related expenses, as a result of injury or harm during study participation.

Refrainment Risks

Possible discomforts or risks associated with not using caffeine include headache, fatigue, decreased concentration, tremors, and irritability.

Possible discomforts or risks associated with not using tobacco include headache, cough, fatigue, and irritability.

Benefits

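### The Phase II and III CO₂ stopping limit, as worded, is met in every test, although Section 7.5 treats reaching it as rare

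*Protocol*

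**What the plan says.** The CO₂ stop for Phases II and III appears in three places in the Protocol.

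- **Section 7.4, text.** The criterion is introduced "as a function of in-mask change in CO₂ concentration from atmospheric levels". The rule follows: "If the in-mask CO₂ concentration is greater than 6% of the atmospheric levels", for more than one minute, and the test ends. The same paragraph says that "subjects will be breathing in a confined space with an expected increase in atmospheric CO₂".
- **Section 7.4, Table 7.** The row for CO₂ in the PAPR uses ≥ and then "6% of atmospheric by volume for a period greater than one minute". It applies to Phases II and III only.
- **Section 7.5.** The risk statement reads "If in the rare event the in-mask CO₂ concentration is greater than 6% of the atmospheric levels", again for more than one minute.

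Section 3.3 (Subject Monitoring) gives the instrument's unit. The analyser will "continuously monitor CO₂ gas (percentage by volume) inside the PAPR facepiece during SWPF testing".

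**The concern.** A limit set at 6% of the atmospheric level lies far below what anyone breathes. Ordinary air is at 100% of that level, and the air in a facepiece can only be higher once the wearer exhales into it. Section 7.4 expects such an increase. A rule that fires at 6% of ambient therefore fires in every test, and this cannot be squared with Section 7.5, which presents it as an uncommon safety event.

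This is the only Table 7 criterion that acts on CO₂ inside the facepiece. The devices concerned are modified to run at or below the certified minimum flow, and Section 7.5 names reduced airflow as a possible cause of rebreathing. If staff follow the text, no subject can complete Phase II or III. If they do not, they are enforcing a number that the protocol does not state, and adherence to the stop cannot be audited.

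**Working it through.** The protocol gives no derivation for the limit, so there is no figure to reproduce. The check is what each reading of the words implies.

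**Inputs from the Protocol**
- Flows (Section 3.3): 170 and 125 L/min for loose-fitting PAPRs, 115 and 100 L/min for tight-fitting PAPRs. Phase III uses 170 and 115 L/min.
- A PAPR supplies surrounding air through a filter by means of a blower (Section 1.0).
- Phase II volume (Section 3.3): "25 subjects x 8 PAPR models x 2 flow rates x 2 regimen replicates = 800 overall SWPF values".
- Phase III volume (Section 3.4 and Appendix A, Phase III calendar): 4 visits, four 30-minute tests per visit.

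**Assumptions, not in the Protocol**
- The particulate filter does not remove CO₂.
- For readings B to D only: ambient CO₂ is 0.04–0.10% by volume, and gas in the facepiece is well mixed.
- For reading B: resting oxygen uptake is 3.5 mL/kg/min, body mass 50–100 kg, and the ratio of CO₂ output to oxygen uptake 0.8.
- For reading C: CO₂ output ranges over 0.15–3 L/min.

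| Reading | Limit, % CO₂ by volume |
|---|---|
| A. 6% of ambient (literal) | 0.06 × 0.04 to 0.06 × 0.10 = 0.0024–0.006 |
| B. 6% relative rise | 1.06 × 0.04 to 1.06 × 0.10 = 0.0424–0.106 |
| C. 6% by volume | 6 |
| D. Ambient plus 6 percentage points | 6.04–6.10 |

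**Reading A.** Supply air is 1.00 × ambient and the limit is 0.06 × ambient. The ratio is 1/0.06 = 16.7 whatever the ambient value. The stop is met before any exhaled CO₂ is counted.

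**Reading B.** The CO₂ output needed is flow × 0.06 × ambient fraction.
- Lowest: 100 L/min × 0.06 × 0.0004 = 2.4 mL/min.
- Highest: 170 L/min × 0.06 × 0.0010 = 10.2 mL/min.
- Resting output: 3.5 × 50 × 0.8 = 140 mL/min to 3.5 × 100 × 0.8 = 280 mL/min.
- Smallest margin: 140/10.2 = 13.7. Even at an ambient of 0.20% the need is 170 L/min × 0.06 × 0.0020 = 20.4 mL/min, and 140/20.4 = 6.9.

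This stop is also met at rest.

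**Reading C.** Mean in-mask CO₂ (%) = ambient + 100 × CO₂ output / flow.
- Lowest: 0.04 + 100 × 0.15/170 = 0.13%.
- Highest: 0.10 + 100 × 3/100 = 3.1%.
- Output needed to reach 6%: from (6 − 0.10)/100 × 100 = 5.9 L/min to (6 − 0.04)/100 × 170 = 10.1 L/min.

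On mean in-mask CO₂ this limit would rarely or never be met. That agrees with Section 7.5, but it is not what the text says. Reading D is practically the same.

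**Number of tests affected under A or B**
- Phase II: 25 × 8 × 2 × 2 = 800.
- Phase III: 25 × 4 × 4 = 400 thirty-minute tests, each made up of two 15-minute regimens.

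**Timing.** Phase II has "ten, 3 minute exercises completed in sequential order"; Phase III exercises last 5 minutes. A condition that must hold for more than one minute, and holds from the start, falls due within the first exercise at the latest.

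**Distance between readings A and C.** 6/0.006 = 1,000 to 6/0.0024 = 2,500 times.

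**The case against.** The strongest reply is that this is a wording slip whose meaning can be recovered. Table 7 adds a by-volume qualifier, the analyser reads percent by volume, and Section 7.5 expects the limit to be reached rarely. All three point to about 6% CO₂ by volume. On that view the counts of 800 and 400 describe an outcome nobody expects, the literal error is on the side of stopping too early, and the other Table 7 stops still protect subjects: their own request, symptoms, oxygen saturation, heart rate and staff discretion. No sample size, power or alpha depends on the limit.

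Much of this stands. The counts show what the sentence entails and do not forecast lost data. The Phase III count rests on the visit calendar; Section 3.4 separately prints 1,200 SWPF values, which does not fit that calendar. The one-minute clock has no stated start, and the sample lines are attached before exercise begins, so the stop could fall due even sooner. Reading B depends on outside assumptions, unlike reading A. The difference between ≥ and > matters little for a continuous reading.

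The reply does not restore the rule. Table 7 keeps the reference to atmospheric alongside the by-volume qualifier, so it does not settle the limit, and 6% CO₂ by volume appears nowhere as a clean statement. The candidate readings run from stopping every test to stopping almost none, and a safety limit should not leave that choice to the operator.

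**Conclusion.** The concern holds: the CO₂ stop is wrong as written. On the literal reading it is met in every Phase II and Phase III test, with supply air at 16.7 times the limit. That result needs only the assumption that the particulate filter does not remove CO₂. The reading as a 6% relative rise is also met at rest, by a factor of at least 13.7 under the assumptions listed. Both contradict Section 7.5. That the sponsor meant 6% CO₂ by volume, or ambient plus 6 points, is a reasonable inference, but the sponsor has to confirm it. The error should be corrected because it concerns a participant-safety threshold. Its practical weight is moderate, since the intent can be guessed and the other stopping criteria continue to apply.

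**What to change.** State one absolute in-facepiece limit in percent CO₂ by volume, with one inequality and the one-minute duration, and use the same sentence in Table 7, Section 7.4 and Section 7.5. The value should be 6% by volume only if the clinical team confirms that this was the intent. It would also help to say whether the limit applies to inspired or mean in-mask CO₂, because at the study flows the mean would be unlikely to reach 6%.

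The cost is amendment wording and a staff re-briefing. No procedure, equipment or subject is added.
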